3.1.4 Randomization and Blinding

3.1.4.1 Wound Selection

One (1) matched wound pair that meets the inclusion criteria (Figure 2) will be selected to be part of the study. Prior to randomization, wounds will be selected and labeled. The Primary Wounds will be labeled P1 & P2. For each subject, one Primary Wound is randomized to B-VEC and the other Primary Wound is randomized to placebo. Up to four (4) Secondary unmatched wounds may be chosen to receive the Remaining Weekly Dose of B-VEC. Secondary wounds will be labeled as they are selected starting with S1, S2, S3 and S4.

Figure 2. Wound Pairing, Labeling, and Selection Example

3.1.4.2 Wound Randomization

Using a pre-generated randomization schedule, primary wounds are randomized to receive either B-VEC or Placebo gel.

3.1.4.3 Blinding and Unblinding

The subjects (including their caregivers) and Investigator as well as Sub-Investigator (conducting outcome related assessments and procedures) will be blinded to the identity of treatment for the Primary Wounds. The unblinded staff, including the pharmacist or authorized designee, and the monitor will remain separate from the primary study team. The unblinded staff will not be involved in any evaluation of the primary outcomes. All un-blinded material will be secured in a secondary locked location, that is not accessible to the primary study team.

The following precautions will be taken to ensure the integrity of the study blind to minimize potential impact on interpretation and of other efficacy and safety measurements:

- In order to maintain the blind, the Remaining Weekly Dose is determined by the Investigator at baseline and is fixed for the duration of the study. Even if a primary wound pair is determined to be closed at a weekly visit, the Remaining Weekly Dose will not change.
- In addition, treatment may be unblinded in a medical emergency. Materials will be provided to the site for emergency unblinding and will be maintained in a secure location where study personnel access is limited.

In the case of a medical emergency necessitating unblinding, the Investigator or designee should, whenever possible, contact the Medical Monitor/Sponsor directly, prior to breaking the blind to discuss if unblinding needs to occur. If unblinding must occur, the designated unblinded staff may provide the information to the

Investigator and this must be captured on the CRF. If unblinded for any reason this must be reported to the Sponsor.

4 Study Populations

4.1 Analysis Populations

4.1.1 Intent-to-Treat (ITT) Population

The intent-to-treat (ITT) population includes subjects whose primary wounds were randomized, regardless of whether they received randomized treatment or not. The ITT population will be used for all the primary and secondary efficacy analyses and baseline summaries.

4.1.2 Safety Population

This population is defined as all subjects who were administered either B-VEC or placebo. The safety population will be used for all the safety analyses.

4.1.3 Modified ITT Population

The modified intent-to-treat (mITT) population includes subjects whose primary wounds were randomized and received B-VEC or placebo treatment with at least one post baseline primary endpoint assessment. The mITT population will be used for all the primary and secondary efficacy sensitivity analyses.

4.1.4 Per-Protocol Population

The per-protocol (PP) population includes all the safety population subjects who completed the study without any major protocol deviations. PP population will be used for all the primary and secondary efficacy sensitivity analyses

5 Overall Statistical Considerations

5.1 General Conventions

The following general comments apply to all statistical analyses and data presentations:

- Summaries will include frequency and percentages for categorical data; frequency and median for ordinal data; and frequency, mean, standard deviation, and median, minimum, and maximum for quantitative data.
- Duration variables (in days) will be calculated using the general formula (end date – start date) +1.
- Change from baseline will be calculated for each subject at the specified time point as the value at the specified time point minus the baseline value.
- Individual subject listings of all data represented on the eCRFs will be provided to facilitate the investigation of tabulated values and to allow for the clinical review of all efficacy and safety parameters.
- Version 9.4 (or higher) of SAS® statistical software package will be used to provide all summaries, listings, graphs, and statistical analyses.

5.2 Baseline Definition

In general, baseline is defined as the value closest to but prior to administration with either B-VEC or placebo (Screening or Visit 1/ Week 1).

5.3 Handling of Missing Data

Missing data will be handled as outlined below:

- All missing and partial dates for adverse events or for medications received after randomization will be queried for a value. If no value can be obtained, substitutions will be made as detailed in [Appendix 2](#). These substitutions will be used in calculations; however, the actual value recorded on the eCRF will be used in all listings.
- A multiple imputation approach, described in section [7.1.6](#), will be used to impute any primary and key secondary efficacy endpoint missing values. The severity and causality assessment for adverse events cannot be missing. Missing data will be queried for a value.

6 Statistical Analysis Methods

6.1 Subject Disposition

The number of subjects included in each of the analysis populations (ie, ITT, Safety, mITT, and PP) will be summarized. A listing will be provided that indicates each subject's inclusion /exclusion from the populations and the reason for exclusion from each of the populations.

The number and percentage of subjects completing the study (defined as receiving at least 1 administration of either treatment and returning for all of the weeks 1 through 26, and SFU Visits), not completing the study, missing each of the Visits, and prematurely discontinuing from treatment will be presented for the ITT, mITT, and PP populations. A listing of all subjects who prematurely discontinued from treatment or not completing the study will be presented, and the primary reason for discontinuation of treatment or not completing the study will be provided.

6.2 Demographics and Baseline Characteristics

The descriptive summaries of subjects' demographic and baseline characteristics are for the safety, ITT, mITT and PP populations. A detailed description of subject disposition will be provided.

The following subject characteristics will be summarized:

- Subject demographics
- Baseline characteristics
- Pre-existing medical conditions

Continuous variables will be summarized using number of observations, mean and standard deviation, median, and minimum and maximum values. Categorical values will be summarized using number of observations and percentages.

Medical History and AEs will be summarized by MedDRA System Organ Class and preferred term.

6.3 Treatment Compliance and Exposure

Exposure summary by treatment group (primary wounds only) will be presented for the Safety, mITT, and PP populations. The distribution of subjects by the total number of weeks on therapy (0 through 26) will be presented. For the Safety population, the summary of exposure will be based on the actual treatment received.

Treatment compliance is defined as the number of wound treatment doses (active and placebo) actually received divided by the number of doses expected ($\times 100$) over the time period defined by the first and last treatment dose dates. Descriptive statistics for treatment compliance and the number and percentage of

subjects at least 90% compliant will be presented by treatment group (primary wounds only) for the Safety, mITT, and PP populations.

7 Efficacy Analyses

All data will be presented using summary statistics or frequency tables, as appropriate, and will be analyzed for superiority comparisons between B-VEC and placebo treatments. The description of the sample will be done using summary statistics (n, mean, standard deviation, median, and maximum/minimum) for continuous data and using frequency statistics (counts and percentages) for categorical data. Hypothesis testing, unless otherwise indicated, will be performed at the 5% significance level (2-sided). All P-values will be rounded to four decimal places; P-values less than 0.0001 will be presented as '<0.0001' in all tables. Unless specifically stated, all confidence intervals will be two-sided with 95% coverage.

Efficacy measures collected pre-dosing at Screening or Visit 1 (Week 1) will be considered as the baseline measurement in this study.

The Sponsor, or their designee, will analyze the data using SAS® Statistical Analysis System Version 9.4 or higher.

7.1 Analysis and Data Conventions

7.1.1 Multi-center Study

The statistical analysis for this multi-center study will use the set of subjects pooled across all centers. Center will not be used as a stratification factor or covariate in the statistical analysis models.

7.1.2 Adjustments for Covariates

No stratification factors were used for randomization and no adjustments for covariates will be used in the efficacy analyses.

7.1.3 Handling of Dropouts or Missing Data

The reason of early study treatment / study discontinuation will be identified, and the percentage of these subjects will be summarized by treatment group.

A multiple imputation approach, described in section 7.1.6, will be used to impute missing values.

7.1.4 Multiple Comparisons/Multiplicity

The primary efficacy endpoint is a single responder outcome during weeks 24 through 26 that will be compared between two treatment groups. Therefore, the primary analysis will not be adjusted for multiple comparisons.

7.1.5 Examination of Subgroups

The treatment effect for the primary and key secondary efficacy endpoints will be examined for the following subgroups:

- Age (≤ 12 years, >12 and ≤ 18 years, >18 years)
- Sex (Male, Female)
- Race (White, African American, additional groups must represent at least 25% of the population if not, will group as 'All Other')

Summaries of the primary and key secondary efficacy variables by treatment group and subgroups will be produced.

7.1.6 Analysis Methods – Multiple imputation

Multiple imputation methods will replace each missing primary efficacy endpoint value with a set of $m=10$ plausible values based on a model predicting values for a missing data point based on available data, assuming a Missing at Random (MAR) missingness mechanism.

This set of values represents the uncertainty about the correct value to be imputed. Each of the 10 complete datasets (generated by SAS PROC MI) will be analyzed by relevant statistical procedures (e.g., SAS PROC FREQ for McNemar Test, SAS PROC LOGISTIC, etc). The results for the 10 datasets will be combined using the method described on p. 115 of Schafer, J.L. (1997)

Prediction model

The prediction model predicts a missing endpoint value based on available data (variables) that may have an influence on that endpoint. The prediction model for the binary primary efficacy endpoint will be a logistic regression model with the following covariates:

- randomized study treatment: B-VEC or placebo
- sex: male or female
- age at baseline (continuous covariate)
- body weight at baseline (continuous covariate)
- race (White, African American, additional groups must represent at least 25% of the population if not, will group as 'All Other')

Algorithm for the multiple imputation of missing values

Within the Bayesian framework, the task of imputing missing values is achieved by drawing random values from the posterior predictive distribution of the missing primary efficacy endpoint data (predicted by the logistic regression prediction model specified above). This posterior predictive distribution is a function of the observed data and regression parameters (or function of regression parameters).

As non-monotone missing pattern may be observed, the fully conditional specification (FCS) method will be used for dealing with arbitrary non-monotone missing data patterns. The FCS is based on an iterative algorithm; at each iteration and for each variable of the prediction model, there is a

- prediction step (P-step): the current (iteration) values of the observed and imputed values are used to derive the predictive distribution of the missing values
- and an imputation step (I-step): updated imputations are generated by draws from the predictive distribution defined by the updated regression model.

When the last variable in the sequence (e.g., the primary efficacy endpoint) has been imputed, the algorithm cycles again through each variable, repeating the chain of regression estimation and imputation draw steps. These cycles are repeated and finally there will be $m=10$ draws from the predictive distribution for each missing primary efficacy endpoint value.

Analyzing multiply imputed datasets

Individual statistical analysis will be performed using the McNemar Test for each of the $m=10$ imputed complete datasets and the results (point estimates and associated standard errors for the study treatment effect) will be stored in a single output file.

Estimation and inference for multiply imputed datasets

As a final step, the $m=10$ estimates and associated standard errors will be combined using the method described on p. 115 of Schafer, J.L. (1997). The chi-square statistics can be either Wald statistics or

likelihood ratio statistics. The chi-square values and the degrees of freedom from all 10 imputed datasets will be used.

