3.1.3 Number of Subjects and Interim Analysis

With 90% power and a two-sided Type 1 error rate of 5%, 24 subjects (i.e., 24 wound pairs) are required for a McNemar's test, assuming a response rate of 75% among wounds randomized to B-VEC and a response rate of 25% among wounds randomized to placebo. These response rates are supported by the results of a Phase 1/2 study in which the response rates for weeks 10 and 12 were 71% and 83% for active and 33% and 14% for placebo, respectively. Because the sample size calculation assumes no correlation within subjects, the estimate is conservative. Any positive correlation will cause an increase in power for the sample size of 24. PASS 2020, "Tests for Two Correlated Proportions (McNemar Test)", was used to calculate the sample size. Because of the small n, the multinomial enumeration was used instead of the normal approximation.

If we assume a 75% response rate among wounds randomized to B-VEC and a 25% response rate among wounds randomized to placebo and we assume independence among the wounds within a subject, we expect a total of 62.5% discordant pairs. Under this scenario, 18.75% of the subjects will have positive responses for both wounds and 18.75% will have negative responses for both wounds:

Expected rates of response and non-response, assuming a 75% response rate for B-VEC treated wounds, a 25% response rate for placebo-treated wounds and no correlation between wounds. The off-diagonals correspond to discordant pairs.

		Placebo		
		Response	Non-response	Total
B-VEC	Response	18.75%	56.25%	75.00%
	Non-response	6.25%	18.75%	25.00%
	Total:	25.00%	75.00%	100%

[figure not shown]
Interim analyses will not be performed for this study.

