7.3 Key Secondary Efficacy Analysis

The key secondary efficacy analyses will be based on the ITT population. The primary efficacy analyses will be repeated for responder wounds that meet any of the following conditions:

- Healed on Week 8 and Week 10, or
- Healed on Week 10 and Week 12.

Only wounds that are healed for at least two (2) consecutive weeks are counted as positive responses. The key secondary endpoint response data will be summarized descriptively by the wound treatment.

The McNemar testing procedure used for the primary endpoint will be repeated for this key secondary endpoint. A multiple imputation approach (details see section [7.1.6](#)) assuming MAR will be used to impute missing endpoint data. If the primary endpoint is statistically significant at a type I rate of 0.05, the same full type I rate of 0.05 will be passed on to evaluate the key secondary endpoint.

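### With only ten imputations and no stated seed, a borderline primary p-value with two or three missing pairs can fall on either side of 0.05 by chance of the seed

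*SAP*

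**What the plan says.** SAP 7.1.6 describes one imputation procedure. Multiple imputation "will replace each missing primary efficacy endpoint value with a set of $m=10$ plausible values" under a missing-at-random assumption, from a logistic model in treatment, sex, age, weight and race. The end of the algorithm description repeats the number: the cycles finish with ten "draws from the predictive distribution for each missing primary efficacy endpoint value". On software, the SAP says: "Each of the 10 complete datasets (generated by SAS PROC MI) will be analyzed by relevant statistical procedures". The ten McNemar results are then pooled by a rule that is cited to a textbook page and not printed.

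SAP 7.2 applies this to the primary endpoint. SAP 7.3 applies it to the key secondary, where a multiple imputation approach "assuming MAR will be used to impute missing endpoint data", and passes the full 0.05 to that endpoint only if the primary is significant. The supplementary analyses in 7.2.1 and 7.3.1 reuse it.

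No seed, number of burn-in cycles or check of Monte Carlo error appears in the SAP or in protocol 8.9. The only version of the primary test without imputation is the observed-data sensitivity analysis in SAP 7.2.1.

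**The concern.** Multiple imputation uses random draws, so its p-value carries simulation error that shrinks as m grows. Ten draws may be enough for a point estimate in a large trial. Here the statistic is built from a small number of discordant pairs and compared with a hard threshold, so the error can matter.

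If it does, two analysts who follow the SAP exactly on the same locked data could reach opposite conclusions on the primary endpoint, and therefore on whether the key secondary may be tested at all. The plan also could not be used to reproduce the reported p-value. With the seed left open, nothing in the plan rules out choosing one after the data are seen. No such intent is suggested; pre-specification exists to remove the possibility.

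**Working it through.** **Inputs from the documents**

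- SAP 3.1.3: "With 90% power and a two-sided Type 1 error rate of 5%, 24 subjects (i.e., 24 wound pairs) are required", "assuming a response rate of 75% among wounds randomized to B-VEC and a response rate of 25% among wounds randomized to placebo", and "the sample size calculation assumes no correlation within subjects". The SAP's table gives discordant cells of 0.75 × 0.75 = 56.25% (B: B-VEC healed only) and 0.25 × 0.25 = 6.25% (C: placebo healed only).
- SAP 7.2: statistic (B − C)² / (B + C) on 1 df, with a continuity correction if B + C < 6.
- SAP 7.1.6: m = 10, seed not stated.

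**Assumptions**

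- Number of missing pairs: one to three in the fixed tables and up to five in the trial simulations.
- Pooling: the standard chi-square combination rule, because the SAP cites its rule without printing it. With d_i the McNemar chi-square in dataset i and r = (1 + 1/m) × the sample variance of √d_i, the pooled value is D = [mean(d) − ((m + 1)/(m − 1)) r] / (1 + r), referred to F with 1 and (m − 1)(1 + 1/r)² df.
- Imputation: treatment-only model with posterior draws, which is simpler than the SAP's. A version with four simulated covariates was run as a check.

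**Step 1. The plan's own figure.** The SAP notes that "the multinomial enumeration was used instead of the normal approximation". Full enumeration with cells 0.5625 / 0.0625 / 0.375 and the exact two-sided McNemar test gives power of 88.8% at 23 pairs and 90.5% at 24. The stated 24 is reproduced. Expected discordant pairs: 0.625 × 24 = 15.

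**Step 2. What one imputed pair does.** Start from 10 v 3: (10 − 3)²/13 = 3.77, p = 0.052. One imputed pair added to B gives 8²/14 = 4.57, p = 0.033. One added to C gives 6²/14 = 2.57, p = 0.109. Each completed dataset therefore moves in coarse jumps across 0.05, and ten such values are combined.

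**Step 3. Spread over seeds, same observed data.** 3,000 seeds per table; the range is the 5th to 95th percentile of p, with the share of seeds significant in brackets.

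| Observed B v C | Missing pairs | m=10 | m=100 | m=1000 |
|---|---|---|---|---|
| 10 v 3 | 3 | 0.031–0.076 (57%) | 0.040–0.053 (83%) | 0.044–0.048 (99.9%) |
| 10 v 3 | 2 | 0.035–0.072 (53%) | 0.044–0.054 (64%) | 0.047–0.050 (89%) |
| 13 v 5 | 3 | 0.034–0.070 (58%) | – | – |
| 13 v 5 | 2 | 0.039–0.071 (43%) | – | – |
| 11 v 4 | 3 | 0.042–0.093 (19%) | – | – |

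A separate run of the first row with 400 seeds gave 0.030–0.077 and 56% at m=10.

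With covariates in the imputation model, 10 v 3 is significant for 57% (two missing) and 67% (three missing) of seeds at m=10. If estimates and standard errors are pooled by Rubin's rules instead, the sensitive table moves to 11 v 4, significant for 62% (two missing) and 67% (three missing) of seeds.

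**Step 4. How often this arises.** Each possible observed table was weighted by its multinomial probability. A table counts as seed-dependent if 5% to 95% of seeds are significant.

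| True rates | Missing pairs | Seed-dependent, m=10 | Two seeds disagree, m=10 | Two seeds disagree, m=1000 |
|---|---|---|---|---|
| 75% v 25% | 2 | 5.9% | 1.9% | 0.3% |
| 75% v 25% | 3 | 7.2% | 2.5% | 0.0% |
| 70% v 30% | 2 | 13.0% | 4.1% | 0.5% |
| 60% v 25% | 3 | 16.8% | 5.9% | 0.0% |

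A separate trial simulation with two to five missing pairs gave m=10 disagreement of 2% to 4% at 75% v 25%, and 4% to 9% at 60–67% v 25–33%.

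**The case against.** The strongest reply is that the example sits on the cut-off. Without imputation 10 v 3 already gives p = 0.052, so any noise will split it. At the design cells, exactly 10 v 3 in 21 pairs has probability 1.8%; the expected split is about 12 v 1. Clear results do not move: 10 v 2 stays significant in at least 99.7% of seeds. This stands, and it limits the weight of the point.

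Second, the number of missing pairs is not in the documents. The endpoint rule also restrains missingness: a wound not healed at Week 24 is a non-responder whatever happened at Weeks 22 and 26, and one healed at Weeks 22 and 24 needs no Week 26 value. With no missing outcomes the issue vanishes. That also stands. Against it, subjects attend weekly for 26 weeks, the endpoint falls at the end, the ITT analysis keeps every randomized subject, and no dropout allowance is stated for the 24. With one pair missing the effect is smaller but present (10 v 3: p from 0.041 to 0.067, 42% of seeds significant).

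Third, the figures depend on the pooling rule assumed. The location of the sensitive tables does depend on it; their existence does not.

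Fourth, m=1000 does not end seed dependence exactly at the boundary: 10 v 3 with two missing pairs still has 89% rather than 100% of seeds significant. That is correct, and it is why the seed is needed as well.

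Finally, the observed-data sensitivity analysis would make a seed-driven result visible. It would not change the confirmatory p-value.

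**Conclusion.** The concern holds. Ten imputations without a stated seed make the primary conclusion depend on the seed when outcomes are missing and the result is close to 0.05. For 10 v 3 with three missing pairs, p runs from about 0.03 to just under 0.08, and little more than half of seeds are significant. Across trials with two or three missing pairs, disagreement between two runs is about 2% to 2.5% at the planned effect and about 4% to 6% at weaker effects.

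This is a loss of precision and reproducibility; no bias or inflation of type I error has been shown. The size rests on the assumed number of missing pairs, the assumed pooling rule and a simplified imputation model. It should be changed because the confirmatory test and the step to the key secondary both depend on it and the remedy is almost free.

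**What to change.** In SAP 7.1.6, replace m=10 with m=1000 in both the opening description and the end of the algorithm, and bring the later references to ten datasets into line. State the PROC MI seed in the SAP before unblinding. Apply both to the primary and key secondary analyses and to every supplementary analysis that reuses 7.1.6. Both parts are needed: the seed makes the result reproducible but leaves it arbitrary, and the larger m removes most of the arbitrariness.

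The same edit could print the pooling formula. 7.1.6 refers both to estimates with standard errors and to chi-square values, and that choice moves borderline p-values about as much as the seed does.

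The cost is a short SAP edit and seconds of computing. Sample size, data collection and trial conduct do not change.

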## 8.7 Efficacy Analyses

### 8.7.1 General Approach

The study has a complete randomized-block design in which each subject serves as a block to receive all of the treatment conditions. In this study, each subject provides at least one pair of target wounds with one wound from each pair being treated with B-VEC and the other wound from each pair with placebo in the primary target wound pair. Efficacy measurements are taken multiple times (or repeatedly) over the on-treatment period from each subject.

All data will be presented using summary statistics or frequency tables, as appropriate, and will be analyzed for superiority comparisons between B-VEC and placebo treatments. The description of the sample will be done using summary statistics (n, mean, standard deviation, median, and maximum/minimum) for continuous data and using frequency statistics (counts and percentages) for categorical data. Hypothesis

testing, unless otherwise indicated, will be performed at the 5% significance level (1-sided). All P-values will be rounded to four decimal places; P-values less than 0.0001 will be presented as '<0.0001' in all tables. Unless specifically stated, all confidence intervals will be two-sided with 95% coverage.

Efficacy measures collected pre-dosing at Screening or Visit 1 (Week 1) will be considered as the baseline measurement in this study.

The Sponsor, or their designee, will analyze the data using SAS® Statistical Analysis System Version 9.1.3 or higher. Detailed descriptions of the statistical analysis methods, data conventions, and sensitivity analysis, as well as handling of missing data for both efficacy and safety measures will be described in detail in the Statistical Analysis Plan (SAP).

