7.2 Primary Efficacy Analysis

The primary efficacy analyses will use the ITT population and the Primary Wound Pair.

The primary endpoint is the proportion of DEB primary wound sites with complete wound healing from baseline in B-VEC-treated and placebo-treated intra-subject wound sites at Weeks 22 and 24 or 24 and 26, as determined by the Investigator. Complete wound healing is defined as 100% wound closure from the exact wound area selected at baseline, specified as skin re-epithelialization without drainage:

The primary endpoint is defined as responder wounds that meet any of the following conditions:

- Healed on Week 22 and Week 24, or
- Healed on Week 24 and Week 26

Only wounds that are healed for at least two (2) consecutive weeks are counted as positive responses. The primary endpoint response data will be summarized descriptively by the wound treatment.

A summary of the outcomes for each member of the Primary Wound Pair can be represented in the following 2x2 table, where each entry represents a subject. T is the total number of subjects in the ITT population and each cell entry is the number of subjects with the corresponding outcomes of the Primary Wounds.

		Placebo		Row total
		Complete Wound Healing	No Complete Wound Healing	
B-VEC	Complete Wound Healing	A	B	N1
	No Complete Wound Healing	C	D	N2
Column total		M1	M2	T

The null hypothesis of interest is the absence of a treatment effect on wound healing and the alternative hypothesis is the presence of a treatment effect on wound healing.

These hypotheses are equivalent to the following null and alternative hypotheses:

Null Hypothesis H0: Prob(B) = Prob(C)

Alternate Hypothesis H1: Prob(B) ≠ Prob(C)

Where Prob(B) and Prob(C) are the probability of the occurrence of discordant pairs B (B-VEC=Positive & PBO=Negative) and C (B-VEC=Negative & PBO=Positive).

The null hypothesis will be tested by a McNemar test statistic using a two-sided type I error rate of 0.05:

$$\chi^2_{\text{McNemar}} = (B - C)^2 / (B + C)$$

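### SAP 7.1.6 imputes a subject's two wounds independently given the covariates; if the wounds are positively correlated and pairs are missing, this weakens the paired McNemar test and pulls the odds ratio toward 1

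*SAP*

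**What the plan says.** SAP 7.1.6 describes the imputation of the primary endpoint this way: "The prediction model for the binary primary efficacy endpoint will be a logistic regression model with the following covariates". The first covariate is "randomized study treatment: B-VEC or placebo"; the others are sex, age, body weight and race. No subject identifier, partner-wound outcome or wound-level variable is listed. The description of the fully conditional specification (FCS) algorithm adds none. SAP 7.3 applies the same method to the key secondary endpoint.

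The design and the analysis are paired. Protocol 8.7.1 states: "The study has a complete randomized-block design in which each subject serves as a block to receive all of the treatment conditions". SAP 7.2 sets out the outcomes "in the following 2x2 table, where each entry represents a subject" and tests (B − C)²/(B + C), where B counts subjects healed on B-VEC only and C counts subjects healed on placebo only. A continuity correction applies when B + C is below 6. The ratio B/C is reported as the effect size.

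On correlation, SAP 3.1.3 plans on none between a subject's wounds and adds: "Any positive correlation will cause an increase in power for the sample size of 24".

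**The concern.** Treatment can vary as a covariate only if each wound is its own row, giving 48 rows for 24 subjects. The other four covariates take the same value for both wounds of a subject. Once they are fixed, nothing in the model links the two wounds, so the imputed outcomes of a pair are independent draws. If only one wound is missing, its observed partner is not used.

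McNemar's test takes its information from discordant pairs. If a subject's wounds tend to heal or fail together, independent draws produce more reversed (C) pairs than the population contains. B + C is then inflated, B/C shrinks and power is lost. Both wounds are assessed at the same visits, so a withdrawal removes the whole pair. The primary population is all randomized subjects, so those pairs are imputed. The primary result also gates the key secondary test (SAP 7.3), and the supplementary analyses in 7.2.1 and 7.3.1 use the same imputation method.

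**Working it through.** **Inputs.** From SAP 3.1.3: "With 90% power and a two-sided Type 1 error rate of 5%, 24 subjects (i.e., 24 wound pairs) are required", "assuming a response rate of 75% among wounds randomized to B-VEC and a response rate of 25% among wounds randomized to placebo", and Phase 1/2 "response rates for weeks 10 and 12 were 71% and 83% for active and 33% and 14% for placebo, respectively". From SAP 7.1.6: m = 10. From SAP 7.2: the test and the B + C < 6 rule. Assumed, because the documents do not give them: the correlation φ, the number of missing pairs, missingness completely at random, and uninformative demographic covariates. The 60% v 30% scenario is hypothetical, to show a weaker effect.

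**1. The plan's own figure.** With zero correlation, P(B) = 0.75 × 0.75 = 0.5625 and P(C) = 0.25 × 0.25 = 0.0625, a total of 62.5% discordant, as the SAP states. Full enumeration of the exact two-sided McNemar test gives power 0.905 at N = 24, the smallest N reaching 90%. The sample size is reproduced. The uncorrected test of SAP 7.2 gives 0.941.

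**2. Reversed pairs.** With healing rates p_B and p_P:

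- both healed: p11 = p_B·p_P + φ·√[p_B(1 − p_B)·p_P(1 − p_P)]
- true reversed rate: p_P − p11
- rate under independent imputation: (1 − p_B)·p_P, whatever φ is

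| Rates | φ | True reversed rate | Imputed reversed rate |
|---|---|---|---|
| 75/25 | 0 | 6.25% | 6.25% |
| 75/25 | 0.17 | 0.25 − (0.1875 + 0.17 × 0.1875) = 3.1% | 6.25% |
| 75/25 | 0.33 (maximum) | 0.25 − 0.25 = 0% | 6.25% |
| 71/33 | 0.33 | 0.33 − (0.2343 + 0.33 × 0.2134) = 2.5% | 0.29 × 0.33 = 9.6% |
| 60/30 | 0.40 | 0.30 − (0.18 + 0.40 × 0.2245) = 3.0% | 0.40 × 0.30 = 12% |

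**3. Odds ratio.** At 75/25 and φ = 1/6, p11 = 0.21875, so P(B) = 0.53125, P(C) = 0.03125 and B/C = 17.0. With 4 of 24 pairs imputed independently, expected B = 20 × 0.53125 + 4 × 0.5625 = 12.875 and expected C = 20 × 0.03125 + 4 × 0.0625 = 0.875, so B/C = 14.7. With 6 pairs imputed it is 12.9375/0.9375 = 13.8.

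**4. Power under the SAP's rules.** This was simulated with 24 subjects, 4 whole pairs missing and m = 10. The SAP model was represented by separate posterior draws per treatment. Pair-level imputation was represented by posterior draws on the four cells of the 2×2 table. The B + C < 6 correction was applied throughout. SAP 7.1.6 says chi-square values are combined by a cited method. The standard combination of chi-square statistics was assumed: with d the ten statistics and r = (1 + 1/m)·var(√d), D = [mean(d) − r(m + 1)/(m − 1)]/(1 + r), referred to an F distribution with 1 and (m − 1)(1 + 1/r)² degrees of freedom.

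| Rates | φ | SAP imputation | Pair-level | Dropping pairs |
|---|---|---|---|---|
| 75/25 | 0 | 0.899 | 0.897 | 0.884 |
| 75/25 | 0.17 | 0.943 | 0.953 | 0.941 |
| 75/25 | 0.33 | 0.983 | 0.991 | 0.979 |
| 71/33 | 0.33 | 0.798 | 0.846 | 0.799 |
| 60/30 | 0.40 | 0.587 | 0.654 | 0.565 |

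The losses against pair-level imputation are 0.8 to 1.0 points at 75/25 with positive correlation, 4.8 points at 71/33 (about 3 at φ = 0.20) and 6.7 points at 60/30. These are simulation estimates, so small differences should not be over-read.

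**5. Type I error.** With 50% healing in both arms, φ = 0.5 and 4 pairs missing, rejection is 2.1% under SAP imputation. At φ = 0 it is 4.8%. Neither exceeds 5%.

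**The case against.** The strongest reply is that the plan assumes zero correlation, and at zero correlation independent draws are correct. That is fair. A reader might infer that the sample size counts on positive correlation; SAP 3.1.3 says the reverse and mentions such correlation only as a gain in power. The zero assumption is called conservative for sample size. It does not justify forcing independence on the imputed pairs.

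A reader might also infer that this imputation is worse than leaving incomplete pairs out. On average, under the SAP's own rules, it is not: the last table shows it about equal to dropping or above it. The stronger reading needs the continuity correction to be left out. At 71/33 with φ about 0.34 and 4 pairs missing, the uncorrected test gives 0.853 for dropping and 0.800 for SAP imputation; with the correction these become 0.800 and 0.804. A single dataset can still go that way. With 20 observed pairs A = 7, B = 6, C = 0, D = 7 and 4 missing, dropping gives 6²/6 = 6, p = 0.014. SAP imputation gives a median p of 0.025 (above 0.05 in 9% of runs) and pair-level imputation 0.0095. Where only one wound of a pair is missing, SAP imputation beats dropping (75/25, φ = 0.17, 4 missing: 0.958 v 0.941), although it still ignores the partner.

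Three further points stand in part. Shared sex, age, weight and race can induce some correlation between imputed wounds, so treating them as uninformative is the unfavourable case. The pair-level figures come from four-cell draws, so the exact FCS logistic proposed below has not been simulated. At the planned rates the power loss is small.

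**Conclusion.** The concern holds as a mismatch between the imputation model and the paired analysis. It needs two conditions: positive correlation between a subject's wounds beyond the listed covariates, and missing endpoint data. With both present, imputed pairs carry too many reversed results, B/C is attenuated and power is lost relative to an imputation that keeps the pair. With 4 of 24 whole pairs missing, the loss is about 1 point at 75/25 (φ 0.17 to 0.33), 3 to 5 points at 71/33 (φ 0.20 to 0.33) and 7 points at 60/30 (φ 0.40). It is nil at zero correlation or with complete data.

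The error is toward a conservative test; no inflation of type I error was found. The sizes rest on assumed correlation and missingness, and on the standard chi-square combination. The change is worth making because it is cheap and the imputed analysis is the primary one. At the planned effect it is unlikely to decide the trial.

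**What to change.** In SAP 7.1.6, build the imputation dataset with one row per subject and two outcome columns, B-VEC wound and placebo wound. Impute each by FCS logistic regression with the other as a predictor. Remove treatment from the covariate list, since the column now carries it. Specify an augmented-likelihood option so that the model still fits when a cell such as C is empty. Keep the subject-level covariates as far as 24 rows allow. Use the same structure for the key secondary endpoint and for the supplementary analyses that rely on these imputations.

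The cost is SAP wording and a few lines of SAS, with no new data or subjects. The drawback is that 24 rows support fewer demographic covariates than 48, which gives up some of the pre-specified predictors behind the missing-at-random assumption. At zero correlation the partner term costs almost nothing (0.897 v 0.899 above).
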